# Protocol

## 1. Project Title

Does dietary supplementation with curcumin maintain or improve physical and cognitive function in aging adults at increased risk for disability?

### Short Title

Supporting Physical Independence and Cognition in Elders (SPICE)

## 3. Abstract

Aging is associated with a progressive decline in cognitive and physical function leading to a loss of independence. A growing body of evidence strongly implicates chronic low-grade systemic inflammation as having a significant role in contributing to sarcopenia, functional decline, and ultimately disability. To date, few therapies have been identified to reduce chronic systemic inflammation and improve functional performance in seniors. Natural compounds represent important and underexplored sources of potential new therapies for improving physical function because of their anti-inflammatory properties. In particular, the natural compound, curcumin, has been shown to have potent anti-inflammatory effects in recent clinical trials. The effect of these compounds on functional outcomes, particularly in older humans (age  $\geq 70$  years) at risk of functional decline, is not well documented. This placebo-controlled RCT tests whether dietary supplementation with curcumin maintains or improves cognitive and physical function in older adults who are at high risk of functional decline due existing (mild) functional impairments and elevated biomarkers of inflammation and explore the association between functional changes and changes in biological indicators of active inflammation.

## 4. Background

a. General Overview. The life expectancy of older Americans continues to increase, with persons aged  $\geq 70$  years representing the fastest growing segment of the US population. While prolongation of life remains an important public health goal, of even greater significance is that extended life should involve preservation of the capacity to live independently and to function well. Therefore, identification of proven interventions to maintain physical function and prevent disability is a major public health challenge. Mobility and activities of daily living represent tasks that are necessary for the maintenance of basic independent functioning. The inability to perform these activities marks a serious decline in functional health, conferring increased risk of institutionalization and death. Many older adults are sedentary. Among this population, many are mobile and free of disability but have elevated levels of pro-inflammatory markers and reductions in mobility marked by slower walking speed, which, in turn, is a key predictor of further decline and of increased risk of mortality. These individuals represent the target population for the proposed intervention.

**b. Causes of Physical Disability in Older Persons.** Although physical disability can be directly caused or aggravated by acute events (stroke and hip fracture) and severe chronic conditions (heart failure, coronary heart disease), a large proportion of mobility disability follows a progressive course over several years in older persons. Specifically, a large and growing number of older adults experience progressive declines in physical function culminating in age-related physical disability with no clear connection to a single disease. Sarcopenia, the progressive loss of muscle mass and strength, has been identified as a common pathway associated with initial onset and progression of physical disability among adults with a variety of disease conditions. This is noteworthy as recent estimates suggest that sarcopenia is present in one quarter of persons aged 65 years or older. Chronic health conditions, such as diabetes and peripheral artery disease, and lifestyle factors, such as poor nutrition and physical inactivity, have strong potential to accelerate sarcopenia progression and ultimately physical disability. This is particularly important as the number of older adults with chronic disease conditions associated with unhealthy lifestyle habits has increased dramatically over the past few decades.

As diverse as the etiologies of physical disability are, a growing body of evidence strongly implicates chronic low-grade systemic inflammation as playing a significant role in contributing to sarcopenia and associated functional decline. In present study, systemic inflammation is defined based on elevations in key pro-inflammatory cytokines, specifically plasma C-reactive protein (CRP), tumor necrosis factor Alpha (TNF- $\alpha$ ), and particularly interleukin-6 (IL-6). Increased levels of systemic inflammation have been shown to be detrimental to skeletal muscle in humans as well as in animal models through direct catabolic effects or through indirect mechanisms (i.e., decreases in GH and IGF-1 concentrations, induction of anorexia). Chronic low-grade systemic inflammation has been found to be inversely associated with IGF-1, and reductions in IGF-1, a main messenger of growth hormone, and is associated with sarcopenia, frailty, and mortality in older adults. Elevated levels of systemic pro-inflammatory cytokines have also been found to be positively associated with cachexia, which suggests inflammation may be involved in the process responsible for the anorexia of aging.

Apoptosis (i.e., programmed cell death) may play a key role in the development of sarcopenia, with cell loss occurring in post-mitotic tissues (such as skeletal muscle). An enhanced apoptotic process has been shown in several clinical conditions negatively affecting muscle mass and function. A major mechanism leading to cellular apoptosis is promoted by the activation of specific signaling pathways, including the death receptor binding of TNF- $\alpha$ . This receptor-mediated pathway promotes the activation of a cascade of caspases (e.g., caspase-8 activates caspase-3 and -7) leading to the proteolysis and cellular breakdown. Moreover, cytokines and reactive oxygen species (ROS) can stimulate cytosolic transcription factor nuclear factor-kappa B (NF- $\kappa$ B) to translocate to the nucleus. Translocation of this protein to the nucleus regulates various pro-oxidant enzymes, such as inducible nitric oxide synthase (iNOS), cyclooxygenase-2 (COX), vascular cell adhesion molecule-1 (VCAM-1), and intercellular adhesion molecule-1 (ICAM-1). Hence, pro-inflammatory cytokine production in various tissues is known to be redox-sensitive and can be activated through an altered redox environment. Below, we review the biological mechanisms through which chronic low-grade systemic inflammation may contribute to functional decline.

**c. Strategies to Reduce Inflammation and Improve Function in Seniors.** Few therapies have been identified to reduce chronic low-grade systemic inflammation and improve functional performance in the elderly. There are currently no FDA-approved medications for the treatment of functional impairment in older adults. Given the increasing number of older adults with elevated levels of systemic inflammation who are at risk for functional decline, new therapies are urgently needed to reduce systemic inflammation levels and improve functional ability in

older adults, particularly among adults 70 years and older. In view of recent evidence from both basic and clinical research which identified chronic, low-grade inflammation as the major risk factor underpinning many diseases, a better understanding of the mechanisms of both natural and pharmaceutical anti-inflammatory agents is essential and beneficial beyond academic curiosity.

Natural agents that can modulate the inflammation process have the potential to improve both cognitive and physical function through a number of biological pathways. Long term treatment of inflammatory disorders with NSAIDs (non-steroidal anti-inflammatory drugs) has the potential of serious side effects such as increased risk of gastrointestinal and cardiovascular disease, increased susceptibility to fracture, opportunistic infections, and peptic ulcers. Given the increasing use of anti-inflammatory agents among older individuals, studies are needed to examine their safety and efficacy.

Some natural compounds, such as curcumin, may have multiple physiological effects due to their anti-inflammatory and anti-oxidant properties. These findings are not unexpected given that curcumin has been found to activate a wide variety of targets, and produces broad, systemic effects that are very similar to caloric restriction, the only method to date that has been found to increase healthy lifespan in multiple species. Below we describe studies supporting the potential use of both of these compounds.

d. Curcumin. Curcumin is the bioactive polyphenolic extract of Turmeric, which has been used to treat inflammatory conditions in India for centuries. Findings over the past few decades indicate that curcumin has a broad range of biological properties, including anti-inflammatory and anti-oxidative properties, directly relevant to human health. In past clinical trials, doses ranging from 1000-2500 mg of curcumin per day have been found to be safe and well tolerated. The anti-inflammatory role of curcumin is supported by both in vitro and in vivo evidence. For example, curcumin has been found to inhibit TNF $\alpha$  -activated NF- $\kappa$  B signaling in adipocytes; thereby reducing cytokine expression. Curcumin's anti-inflammatory effects may be due in part to its ability to upregulate expression of peroxisome proliferator-activated receptor gamma (PPAR- $\gamma$ ). Small scale pilot trials have found supplementation with low doses of curcumin (i.e., 20 mg per day) was effective in reducing plasma fibrinogen levels and apolipoprotein B in patients with elevated cardiovascular risk factors. Most recently, supplementation with curcumin at a dose of 500 mg per day over an eight week period was found to significantly lower CRP levels in patients with rheumatoid arthritis.

## **5. Specific Aims:**

### Overall objectives:

- (1) to demonstrate the feasibility, acceptability, and efficacy of the proposed intervention in older adults;
- (2) to examine the biological effects of the intervention on functional performance and inflammatory processes (Specific Aims); and
- (3) to determine the effect size of intervention on key outcomes for sample size calculations for future RCTs.

### Specific Aims:

Specific Aim 1 - To examine the effects of dietary supplementation with curcumin on changes in physical function (walking speed, muscle fatigue, and grip strength) and in

self-reported physical activity

*Hypothesis 1 – Dietary supplementation with curcumin will maintain or improve walking speed, muscle fatigue, strength, and physical activity compared to controls.*

*Specific Aim 2 – To examine the effects of dietary supplementation with curcumin on cognitive performance (attention, memory), and pain symptoms.*

*Hypothesis 2 - Dietary supplementation with curcumin will maintain or improve attention and memory and reduce pain symptoms.*

*Specific Aim 3 – To examine the effects of dietary supplementation with curcumin on markers of systemic inflammation*

*Hypothesis 3 - Dietary supplementation with curcumin will decrease levels of IL-6 and of other systemic and cellular biomarkers of inflammation*

## 6. Research Plan

### Design

The study will be a randomized, placebo-controlled, repeated measures clinical trial to examine whether supplementation with curcumin is associated with the following outcomes in 24 moderately functioning older adults (age  $\geq 70$  years) with elevated levels of inflammation (defined as IL-6  $> 2.0$  pg/mL):

- (1) Improvement in physical function and increase in physical activity,
- (2) Improvement in cognitive performance,
- (3) Improvement in pain symptoms, and
- (4) Reductions in systemic inflammatory biomarkers.

### Study Population

The RCT will include 24 moderately functioning, sedentary adults age 70 years or older with elevated levels of systemic inflammation but without overt disease conditions. We estimate that up to 324 potential participants will undergo screening procedures to identify 24 persons eligible for enrollment in the RCT.

Based on our previous studies, we anticipate that the average age of participants will be approximately 77.0 years, and that approximately 20% will be African Americans. In general, participants will have a relative low prevalence of comorbid diseases.

The key inclusion criteria are the following:

- (1) Age  $\geq 70$  years;
- (2) Mild to moderate physical impairment (Short Physical Performance Battery score  $\leq 10$ );
- (3) Sedentary lifestyle ( $< 120$  min per week of moderate intensity physical activity);
- (4) Chronic low-grade inflammation measured by IL-6  $> 2.5$  pg/ml. To minimize within person variability, IL-6 is the average of 2 measures taken 1-3 weeks apart at screening visits

See Table 1 for a complete list of eligibility criteria.

**Table 1. Inclusion and Exclusion Criteria**

**Inclusion Criteria**

- Age
- Mild to moderate physical impairment (Short Physical Performance Battery score  $\leq 10$ );
- Sedentary lifestyle (< 120 min per week of moderate intensity physical activity);
- IL-6 > 2.5 pg/mL;
- Willingness and ability to give informed consent
- Willingness to be randomized to the intervention groups
- Availability for participation through duration of study

**Exclusion Criteria (General)**

- Failure or inability to provide informed consent
- Residence in a Skilled Nursing Facility (SNF); residence in an Assisted Living Facility (ALF) or independent housing is allowed
- Self-reported inability to walk one block;
- Unable to communicate because of severe hearing loss or speech disorder
- Clinically significant depression (CES-D score > 20)
- Severe cardiac disease, including NYHA Class III or IV congestive heart failure, clinically significant aortic stenosis, history of cardiac arrest, use of a cardiac defibrillator, or uncontrolled angina;
- Severe pulmonary disease, pneumonitis or interstitial lung disease;
- Severe rheumatologic or orthopedic diseases (e.g., awaiting joint replacement, active inflammatory disease);
- Neurological conditions that cause impaired muscle function or mobility (e.g., Parkinson's Disease, multiple sclerosis, ALS)
- Other significant co-morbid medical disease (e.g. renal failure with eGFR < 24 ml/minute or on hemodialysis) or severe psychiatric disorder (e.g. bipolar, schizophrenia);
- Terminal illness with life expectancy less than 12 months, as determined by a physician;
- Excessive alcohol use, defined as more than 5 drinks/day for males or more than 4 drinks/day for females, or more than 14 drinks per week;
- Current smoker or less than 3 years smoking cessation
- Participating in another clinical trial or receiving an investigational product within 3 months prior to screening/enrollment.

**Exclusion Criteria (Curcumin-related)**

- Diabetes mellitus currently taking medications to lower blood glucose (oral or by injection)
- Current use of anticoagulant or anti-platelet medications (aspirin 81 mg daily is allowed)
- Congenital or acquired bleeding disorders
- Cholelithiasis or other gall bladder or biliary tract disease
- Chronic gastrointestinal blood loss or iron deficiency (serum ferritin < 12 ng/mL, with or without anemia)
- History of estrogen-sensitive conditions including breast, uterine, and ovarian cancers; endometriosis; and uterine fibroids
- History of Tuberculosis (TB), HIV, Hepatitis B or C, or other disease potentially compromising immune function

- Current use of:
  - medications targeting immune or inflammatory function (e.g., sulfasalazine, systemic corticosteroids)
  - anabolic medications (e.g., growth hormone, testosterone)
  - monoamine oxidase inhibitors (e.g., phenelzine, selegiline, tranylcypromine)
  - anticholinesterase inhibitors (e.g., donepezil, rivastigmine, galantamine)

### **Temporary Exclusion Criteria**

- Acute infection (urinary, respiratory, other) or hospitalization within 1 month
- Myocardial infarction, CABG, or valve replacement within past 6 months
- Pulmonary embolism or deep venous thrombosis within past 6 months
- Stroke, hip fracture, hip or knee replacement, or spinal surgery within past 4 months
- Receiving physical therapy for gait, balance, or other lower extremity training

### **Recruitment and Initial (Telephone) Pre-Screening**

Potential participants will be recruited from the general population in the North/Central Florida region through:

- (1) IRB-approved advertisements providing basic information about the study and inviting potential participants to call for additional information;
- (2) Contact of potential participants who are enrolled in the Claude D. Pepper Recruitment Registry (IRB#417-2007) by Registry staff;
- (3) Contact of potential participants who are enrolled in Community Engagement and Research Program – Health Street (IRB #265-2011) by Health Street staff; and
- (4) Contact of participants in previous IOA studies who have given consent for re-contact about future studies by Study Coordinators.

Those who express interest will participate in a telephone pre-screening interview to assure basic eligibility criteria are met and exclusion criteria are identified. The interview is designed in a manner that does not collect specific PHI and is conducted by an IRB-approved script. Those who remain eligible after completing the telephone interview are invited to attend in-person screening visit prior to enrollment.

### **In-Person Screening (Screening Visits 1 and 2)**

At Screening Visit 1, participants will be asked to give written informed consent for in-person screening tests and will then be evaluated for cardiovascular and other major diseases by a health review. The health review consists of a review of criteria in the telephone screen, medical and hospital admission history, medication inventory, and physical exam including blood pressure, pulse, weight, and waist circumference.

Short Physical Performance Battery (SPPB) will be performed and the Physical Activity Questionnaire will be administered.

Mini Mental Status Exam (MMSE) and Center for Epidemiological Studies – Depression Scale (CES-D) will be administered to identify potential participants with cognitive dysfunction or

clinically significant depression that would preclude participation. Participants will also provide a blood sample for additional eligibility requirements and participant safety measures.

Approximately 60 ml of blood will be drawn for laboratory tests to assure eligibility (complete metabolic panel, CBC with differential, serum ferritin, and IL-6).

Results of Screening Visit 1 will be reviewed by the PI or his designee. . At this time a copy of the Informed Consent document for the main study will be provided, to allow adequate opportunity for review and consideration before the baseline visit when consent for the main study is obtained. Ineligibles will be contacted by the Study Coordinator for an explanation of ineligibility and will receive a copy of abnormal laboratory results.

### **Enrollment and Randomization**

24 eligible participants will be enrolled and randomized to allow for 6 participant failures or withdrawals

At the baseline visit, the Informed Consent document for the RCT will be reviewed with the potential participant and written consent obtained. Participants will undergo a battery of physical performance tests (400-meter walk; short physical performance battery, grip strength and endurance), formal tests of cognitive function, and a blood draw of about 60 ml (See Table 1). Quality of Life and pain will be assessed with the AM-PAC, the SF-36, and the Brief Pain Inventory (BPI). Self-report of physical activity and dietary fat intake will be obtained through brief questionnaires (RAPA and Block High Fat screen).

Participants will then be randomized to receive either curcumin (1000 mg/day; n = 15) or placebo (microcrystalline cellulose; n=15) for a three-month period. The study drug will be provided for the first month according to randomization.

Participants in both groups will be instructed to return to the research center every month for the duration of the three-month trial. At the monthly visits, compliance with the supplementation regimen for the previous month will be assessed by pill count and participants will be provided with another month's supply of study medication according to initial randomization. Participants will be queried about any adverse events they experienced since their previous visit and any medical history updates they may need to provide. Additionally, blood samples will be obtained (chemistry 15 panel and complete blood count) to ensure that no adverse changes have occurred since their previous visit.

To enhance retention and to ensure participant safety, participants will receive bi-weekly telephone calls throughout the intervention period to ascertain adverse events and express appreciation for participation.

Following the three month supplementation period (Month 3 visit), participants will complete a post-treatment assessment including the battery of physical performance tests (400-meter walk, short physical performance battery, grip strength and endurance); cognitive function tests; questionnaires for quality of life, pain symptoms, and physical activity; and a blood draw of approximately 60 ml (See Table 2).

Approximately 3-4 weeks after the Month 3 visit (at Week 15 – 16), participants will receive a final telephone call to ascertain any late adverse events, discuss any abnormalities from the final safety lab results, and express appreciation for participation.

Table 2. Study Visit Schedule Visit Type	Phone screen (pre-screening)	Screening visit 1		Baseline visit	Week 2	1-Month Visit	Week 6	2-Month Visit	Week 10	3-Month visit	Week 15-16
	Basic eligibility screening	X	X								
Informed Consent (Screening)		X									
Health review and physical examination (including BP, pulse, weight, height, waist circumference)		X									
Medical History and Concomitant Medication		X									
Update Medical History and Concomitant Medication Info				X	X	X	X	X	X	X	
BP, pulse, height and weight, waist circumference		X		X	X	X	X	X	X	X	
MMSE, CES-D		X									
Physical Activity Questionnaire (RAPA)				X						X	
SPPB (including 4 m walk test)		X		X						X	
Phlebotomy		X		X	X	X	X	X	X	X	
IL-6		X								X	
Additional exploratory inflammatory markers (TBD)				X						X	
CBC and Comprehensive Metabolic Panel (CMP) (Safety blood tests)		X		X	X	X	X	X	X	X	
Informed Consent (Main Study), enrollment, and randomization				X							
400 m walk test				X						X	
Isokinetic dynamometry of knee flexors and extensors				X						X	
Isometric hand grip strength				X						X	
Cognitive Function Tests (NIH Toolbox)				X						X	
Quality of Life (AM-PAC, SF-36)				X						X	
Brief Pain Inventory				X						X	
Dietary Fat questionnaire (Block)				X							
Dispense study drug				X	X	X	X	X	X	X	
Scheduled phone call					X	X	X	X	X	X	X
Assess compliance, query adverse effects and events						X	X	X	X	X	X

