## **Statistical Analyses**

Sample size estimates for pilot studies are inherently difficult because by intent, a pilot study is meant to include a smaller sample than a fully powered study. The enrollment sample of 15 participants in the intervention group and 15 participants in the placebo group (allowing for at least 12 evaluable participants in each group after the expected 20% loss due to attrition) is intended to provide sufficient data to indicate feasibility of a larger study and to provide descriptive estimates of effects. Additionally, it will provide for nominal estimation (using a 95% confidence interval) of the mean changes in the inflammatory marker, IL-6, the primary outcome of this pilot.

Feasibility and acceptability of the proposed intervention in older adults will be evaluated by process variables including number of participants completing the study; medication compliance, number and severity of adverse events, and changes in Quality of Life attributable to study participation.

Efficacy will be assessed as effects of the intervention on functional performance (physical and cognitive measures; pain perception, and inflammatory processes (Specific Aims). The following outcomes will be evaluated: physical function (walking speed, muscle fatigue); cognitive function (attention, executive, and memory function); pain (self-report); and systemic inflammation (IL-6, CRP, TNF $\alpha$ , and novel markers)

For each outcome, we will take the value of that outcome after the 3-month supplementation period minus the value at baseline for each participant. Summary statistics and 95% confidence intervals will be provided for within group changes as well as between group differences.

Effect size of intervention on key outcomes for sample size calculations in the planning of a larger RCT. Based on a sample size of 15 per group and 20% attrition, we have 80% power to detect a between group difference of effect size 1.2. Specifically, if we use the root mean squared error from LIFE-P (adjusted for baseline log(IL-6) and treatment) of 0.52 for log(IL-6), then we can detect a mean difference of 0.62 (on the log scale) or equivalently the difference between 4.20 and 2.26 pg/ml (or a 46% difference). And for selection based on walking speed change, we used a within group standard deviation of 0.25, which leads to a detectable mean difference of 0.3 m/s.

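### The protocol gives two numbers to randomise, 24 and 15 + 15 = 30; the stated precision and power fit 30 with 20% attrition, but fit 24 only with no losses

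*Combined protocol and SAP*

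**What the plan says.** Under 6. Research Plan, the Design section describes the trial as examining "outcomes in 24 moderately functioning older adults". The Study Population section repeats 24 as the trial size and says that up to 324 people will be screened "to identify 24 persons eligible for enrollment in the RCT". Enrollment and Randomization begins: "24 eligible participants will be enrolled and randomized to allow for 6 participant failures or withdrawals".

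Later in that same section, participants are randomised to "curcumin (1000 mg/day; n = 15) or placebo (microcrystalline cellulose; n=15", that is, 30 in total. The Statistical Analyses section agrees with 30: "The enrollment sample of 15 participants in the intervention group and 15 participants in the placebo group". It describes this number as "allowing for at least 12 evaluable participants in each group after the expected 20% loss due to attrition". Its power statement has the same basis: "Based on a sample size of 15 per group and 20% attrition, we have 80% power to detect a between group difference". The difference in question is a standardised effect of 1.2, which the section translates into 0.62 on the log IL-6 scale (a 46% difference) and 0.3 m/s in walking speed.

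The planned analysis is descriptive: "Summary statistics and 95% confidence intervals will be provided for within group changes as well as between group differences". IL-6 is named as the primary outcome. No significance test, decision rule or alpha is stated.

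**The concern.** Twenty-four randomised participants cannot be split 15 and 15, so the Enrollment and Randomization section contradicts itself, and the Design and Study Population sections contradict Statistical Analyses. The loss allowance conflicts as well. Six losses from 30 is 20%, which matches the stated attrition, but six from 24 is 25% and leaves 18 rather than 24.

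The number to randomise is a basic operating figure. If 30 is intended, staff who follow the opening line of Enrollment and Randomization stop six short. If 24 is intended, the arm sizes and the evaluable number are wrong, and the confidence intervals will be wider than the plan implies once the losses it expects occur. The pilot is meant to show feasibility, partly through the number completing, and to supply effect sizes for planning a larger trial. Both uses need a defined number randomised.

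**Working it through.** **Counts**

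- Version A (Design; Study Population; first line of Enrollment and Randomization): 24 randomised, 24 − 6 = 18 evaluable, or 9 per arm if losses are balanced. Loss rate 6/24 = 25%.
- Version B (arm sizes in Enrollment and Randomization; Statistical Analyses): 15 + 15 = 30 randomised, 30 × 0.80 = 24 evaluable, or 12 per arm. Loss rate 6/30 = 20%.
- Version A total with Version B loss rate: 24 × 0.80 = 19.2, about 19 evaluable, or 10 and 9.

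**Inputs for precision and power**

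From Statistical Analyses: effect size d = 1.2; planning SD 0.52 for log IL-6; planning SD 0.25 for walking speed. Assumed: two-sample t-test with two-sided alpha 0.05. This reproduces the stated 80%. A one-sided 0.05 test with 12 per arm gives 88.5% and does not.

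**Formulas**

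- Power: the probability that a noncentral t variable with n1 + n2 − 2 degrees of freedom and noncentrality d / √(1/n1 + 1/n2) exceeds the two-sided 5% critical value.
- Between-group 95% CI half-width, in SD: t(0.975, n1 + n2 − 2) × √(1/n1 + 1/n2).
- Within-group 95% CI half-width, in SD: t(0.975, n − 1) / √n.

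**The plan's own figures, 12 and 12 evaluable**

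- Power for d = 1.2 is 80.2% (stated 80%). Detectable d at 80% power is 1.197 (stated 1.2).
- IL-6: 0.52 × 1.197 = 0.622 log units; 1 − exp(−0.622) = 46% (stated 0.62 and 46%). The stated pair 4.20 and 2.26 pg/ml gives 1 − 2.26/4.20 = 46%.
- Walking speed: 0.25 × 1.197 = 0.30 m/s (stated 0.3).

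All of them reproduce, so Statistical Analyses is sound for 30 randomised with 20% attrition.

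**Alternatives**

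| Randomised and lost | Evaluable | Power, d = 1.2 | Detectable d | Between-group half-width (SD) |
|---|---|---|---|---|
| 30, 20% lost | 12 / 12 | 80.2% | 1.20 | 0.85 |
| 24, none lost | 12 / 12 | 80.2% | 1.20 | 0.85 |
| 24, 20% lost | 10 / 9 | 69.2% | 1.37 | 0.97 |
| 24, 6 lost evenly | 9 / 9 | 66.7% | 1.41 | 1.00 |
| 24, 6 lost from one arm | 12 / 6 | 61.6% | 1.49 | 1.06 |

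For 9 per arm against 12:

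- Between-group half-width: 0.999 / 0.847 = 1.18, so 18% wider.
- Within-group half-width: 0.769 / 0.635 = 1.21, so 21% wider.
- Detectable differences on the plan's SDs: 0.52 × 1.407 = 0.732, and 1 − exp(−0.732) = 52% in IL-6; 0.25 × 1.407 = 0.35 m/s.

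The 0.52 is a baseline-adjusted error on the log scale, whereas the planned analysis is a change score with no log transformation or adjustment stated. The IL-6 figure is therefore only a like-for-like restatement.

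**A possible origin (inference only)**

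The reference list runs (29), (24), (31), and the Background citations run 28, 29, 24, 31. The page ranges of references 2 and 32 (1295-1248 and 625-624) run backwards, but run forwards if 24 is read as 30 (1295-1308 and 625-630). This suggests that 30 was replaced by 24 in the file. The replacement was not total, because a 30 cc blood draw survives under Outcome Measures. The pattern would fit an accident, or a deliberate cut that left the 15s unchanged.

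**The case against.** The strongest reply is that the documents lean clearly towards 30. The arm sizes, the allowance of 6, the 20% rate, the 12 evaluable per arm and the power all agree with 30 randomised and 24 evaluable; only the bare totals say 24. On this reading 24 is the evaluable target and the error is one of labelling. That may well be what was meant, but the text calls the 24 both enrolled and randomised, and a deliberate reduction to 24 cannot be ruled out. Under either reading some sections have to change.

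Three narrower points stand as qualifications:

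- The decline from 24 is gradual. One loss (11 and 12) gives 78.3% power and a detectable d of 1.23. The no-losses condition is exact for the 12 evaluable per arm and less sharp for power.
- If 24 was a later cut, the 6 may be left over from 30. The 20% rate then applies, so the fair range is about 67% to 69% power and 0.97 to 1.00 SD. The 12 / 6 split is an extreme.
- The reference-list pattern could have other causes, such as typing or PDF-reading errors, and does not decide between the totals. The contradiction stands without it.

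That this is a pilot lowers the weight of the power figures, but does not remove the need for one enrolment number.

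**Conclusion.** The concern holds. The conflict between 24 and 30 is literal and rests on no statistical assumption. The stated evaluable number, power and detectable differences are correct for 30 randomised with 20% attrition. For 24 they are met in full only if nobody is lost, which contradicts the losses the plan itself expects. With those losses, the between-group interval half-width is 0.97 to 1.00 SD instead of 0.85, and power for d = 1.2 is 67% to 69% instead of 80%, assuming a two-sample t-test at two-sided 0.05 and near-balanced losses. The inconsistent enrolment target and the loss of precision are the main consequences; power is secondary. This must be corrected.

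**What to change.** State one randomised number, one loss allowance and one evaluable number, and align Design, Study Population, Enrollment and Randomization, and Statistical Analyses.

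- **If 30 is intended:** change 24 to 30 randomised (24 evaluable) in the first three sections. The power statement stands. Cost: wording, plus up to six more participants if recruitment has worked to 24.
- **If 24 is intended:** change the arms to 12 + 12 in Enrollment and Randomization and in Statistical Analyses, and choose between 6 losses (25%) and 20% attrition. With 6 losses, state about 9 evaluable per arm, a between-group 95% CI half-width of about 1.00 SD, and either power of about 67% for d = 1.2 or a detectable d of about 1.4. If detectable differences are kept in outcome units (about 52% in IL-6 and 0.35 m/s), say that the IL-6 figure uses a baseline-adjusted log-scale SD. Cost: wording only, with less favourable precision and power.

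In both cases state the alpha and its sidedness. Also check the other instances of 24 against the approved source, for example the 324 to be screened; these are not claimed to be errors.
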